6.1.2. Primary Safety Endpoints

Safety endpoint data will be summarized according to vaccine received. The safety population at each corresponding dose will be used for the analysis for each vaccination.

6.1.2.1. Local Reactions and Systemic Events

The derived variables for each local reaction, systemic event, any local reaction, and any systemic event (ie, swelling, redness, pain at the injection site, fever, vomiting, headache, fatigue, new or worsening muscle pain, new or worsening joint pain, any local reaction, any systemic event) occurring on CCI any day during Day 1 to Day 7 following vaccination will be summarized. The number and percentage of subjects reporting a reaction/event on each day and on any day and the associated 95% Clopper-Pearson CIs will be displayed for each vaccine group.

The presence and maximum severity of each reaction/event and any reaction/event within 7 days (over all days [Days 1-7]) after vaccination will be summarized through proportions of subjects, percentages, and associated 95% Clopper-Pearson CIs.

For each local reaction and systemic event, the maximum duration of each reaction/event will be descriptively summarized by vaccine group. Only subjects experiencing the reaction/event will be included in the analysis. The onset day of each reaction/event will also be summarized for each vaccine group.

All of the above data summaries will be displayed for each vaccination by vaccine group as well as after any vaccination for the presence on each day and maximum severity endpoints.

An overall listing of reactogenicity data and a separate listing of all severe and Grade 4 local reactions and systemic events will be provided.

6.1.2.2. Adverse Events and Serious Adverse Events

The number and percentage of subjects experiencing at least 1 AE/SAE and the number of events will be descriptively summarized by vaccine group for the overall safety population.

Tier 1 and tier 2 events, as defined in Section 3.7.1, will present the proportion of AEs observed in each vaccine group along with the point estimates and associated 95% CIs of the risk difference (the difference of incidence rates) between *C difficile* vaccine and placebo. For both tier 1 and tier 2, the 95% CIs will be calculated using the Miettinen and Nurminen method described in Section 5.2.1.2. The p-value from the Miettinen and Nurminen method will be presented for tier 1 events only.

AE and SAE displays will be sorted in descending order of point estimates of risk difference within system organ class.

Separate listings of AEs and SAEs will also be provided.

6.2. Secondary Efficacy Endpoints

The secondary efficacy endpoints will be analyzed only at the final analysis. All VEs will be estimated using the same method as done for the primary efficacy endpoints, with adjusted type I error. Case-level variables for each endpoint have been defined in [Section 5.2.1.1](#).

The analyses for the secondary objectives are outlined in Table 18 and the evaluable and mITT population will be used for the analysis. The assessment criteria for the secondary objective evaluation are listed below:

- For evaluating *C difficile* vaccine in reducing the incidence of CDI cases (VE analysis), the lower limit (LL) of 98.2% CI for VE >0.
- For evaluating the efficacy of Pfizer’s *C difficile* vaccine in reducing the severity of CDI in terms of the duration, the upper limit (UL) of 2-sided 98.2% CI < 0 for the difference in mean duration of CDI between the *C difficile* vaccine group and the placebo group (*C difficile* vaccine group – placebo group).
- For evaluating the efficacy of Pfizer’s *C difficile* vaccine in reducing the severity of CDI in terms of the risk ratio, the UL of 2-sided 98.2% CI < 1.0 for the ratio of the proportion of subjects experiencing CDI who have a non-protocol-related medically attended visit in the *C difficile* vaccine group to the proportion of the subjects in the placebo group.

Table 18. Final Analysis for Secondary Objectives – Vaccine Efficacy (Point Estimate and 98.2% CI)

Objective	Case Definition	Time Period for Case Accrual	Analysis Population(s)	Parameter for Secondary Efficacy Endpoint
3-Dose Family (assessments will be done sequentially)				
VE in reducing the incidence of all CDI cases	1 and 2	14 days after Dose 3 to end of surveillance period/Day of Dose 3 to end of surveillance period	PP-3/mITT-3	Incidence of CDI as defined by case definitions 1 and 2
VE in reducing the severity of CDI	1	14 days after Dose 3 to end of surveillance period/Day of Dose 3 to end of surveillance period	PP-3/mITT-3	Mean and median time to resolution of case in subjects who had first primary episodes of CDI and difference in mean time to resolution
VE in reducing the severity of CDI	1	14 days after Dose 3 to end of surveillance period/Day of Dose 3 to end of surveillance period	PP-3/mITT-3	Proportion and ratio of proportions of required non-protocol-related medical attention/visits in subjects who had first primary episodes of CDI from C difficile vaccine group and placebo group

Table 18. Final Analysis for Secondary Objectives – Vaccine Efficacy (Point Estimate and 98.2% CI)

Objective	Case Definition	Time Period for Case Accrual	Analysis Population(s)	Parameter for Secondary Efficacy Endpoint
VE in reducing the incidence of recurrent CDI	2	14 days after Dose 3 to end of surveillance period/Day of Dose 3 to end of surveillance period	PP-3/mITT-3	Incidence of recurrent CDI as defined by case definition 2
At-Least-2-Dose/Only-2-Dose Family (assessments will be done sequentially)				
VE in reducing the incidence of all CDI cases	1 and 2	14 days after Dose 2 to end of surveillance period/Day of Dose 2 to end of surveillance period	PP-2/mITT-2	Incidence of CDI as defined by case definitions 1 and 2
VE in reducing the incidence of recurrent CDI	2	14 days after Dose 2 to end of surveillance period/Day of Dose 2 to end of surveillance period	PP-2/mITT-2	Incidence of recurrent CDI as defined by case definition 2
VE in reducing the incidence of primary CDI	1	14 days after Dose 2 to end of surveillance period before Dose 3 ^a /Day of Dose 2 to end of surveillance period before Dose 3 ^a	PP-2/mITT-2	Incidence of first primary CDI as defined by case definition 1
VE in reducing the incidence of recurrent CDI	2	14 days after Dose 2 to end of surveillance period before Dose 3 ^a /Day of Dose 2 to end of surveillance period before Dose 3 ^a	PP-2/mITT-2	Incidence recurrent CDI as defined by case definition 2

Abbreviations: CDI = *Clostridium difficile* infection; PP = per-protocol; VE = vaccine efficacy.

Note: All evaluations will be performed as detailed above. Interpretation of results will follow a staged approach dependent on success of the preceding evaluation. Evaluation order will apply to both the 3-dose family and the at-least-2-dose/only-2-dose family.

- a. End of surveillance period before Dose 3 is the day of the third dose or the day the third dose was expected (168 days after Dose 2) for subjects who received only 2 doses.

For the analysis of multiple events, the mean cumulative function (MCF) for number of events will be estimated by the proportional means model (PROC PHREG procedure from SAS) to compute the regression parameter estimates by maximizing a partial likelihood.⁶ Then the VE will be estimated by 1 minus the estimated hazard ratio.

CCI [REDACTED]

[REDACTED]

[REDACTED]

CCI [REDACTED]

CCI [REDACTED]

[REDACTED]

CCI [REDACTED]

CCI [REDACTED]	[REDACTED]	[REDACTED]	[REDACTED]	[REDACTED]
[REDACTED]	[REDACTED]	[REDACTED]	[REDACTED]	[REDACTED]
[REDACTED]	[REDACTED]	[REDACTED]	[REDACTED]	[REDACTED]
[REDACTED]	[REDACTED]	[REDACTED]	[REDACTED]	[REDACTED]
[REDACTED]	[REDACTED]	[REDACTED]	[REDACTED]	[REDACTED]
[REDACTED]	[REDACTED]	[REDACTED]	[REDACTED]	[REDACTED]

CCI [REDACTED]

CCI [REDACTED]

[REDACTED]

CCI [REDACTED]

CCI	[REDACTED]	[REDACTED]	[REDACTED]	[REDACTED]	[REDACTED]
[REDACTED]	[REDACTED]	[REDACTED]	[REDACTED]	[REDACTED]	[REDACTED]
[REDACTED]	[REDACTED]	[REDACTED]	[REDACTED]	[REDACTED]	[REDACTED]

CCI [REDACTED]

CCI [REDACTED]

[REDACTED]	[REDACTED]
[REDACTED]	[REDACTED]
[REDACTED]	[REDACTED]
[REDACTED]	[REDACTED]
[REDACTED]	[REDACTED]
[REDACTED]	[REDACTED]
[REDACTED]	[REDACTED]
[REDACTED]	[REDACTED]
[REDACTED]	[REDACTED]
[REDACTED]	[REDACTED]

[REDACTED]

CCI [Redacted]

[Redacted]

[Redacted]

CCI [Redacted]

CCI [Redacted]	[Redacted]	[Redacted]	[Redacted]	[Redacted]
[Redacted]	[Redacted]	[Redacted]	[Redacted]	[Redacted]
[Redacted]	[Redacted]	[Redacted]	[Redacted]	[Redacted]

CCI [Redacted]

CCI [Redacted]

CCI [Redacted]

CCI [Redacted]

CCI [Redacted]

[Redacted]

CCI

A large black rectangular redaction box covering the majority of the page content.

CCI

A smaller black rectangular redaction box.

CCI

CCI

A black rectangular redaction box.A black rectangular redaction box.A small black rectangular redaction box.

CCI [Redacted]

CCI [Redacted]

[Redacted]

CCI [Redacted]

CCI [Redacted]

[Redacted]	[Redacted]	[Redacted]	[Redacted]	[Redacted]
[Redacted]	[Redacted]	[Redacted]	[Redacted]	[Redacted]

[Redacted]

CCI [Redacted]

CCI [Redacted]

[Redacted]

CCI [REDACTED]

CCI [REDACTED]

[REDACTED]	[REDACTED]	[REDACTED]	[REDACTED]	[REDACTED]
[REDACTED]	[REDACTED]	[REDACTED]	[REDACTED]	[REDACTED]

[REDACTED]

[REDACTED]

CCI [REDACTED]

[REDACTED]

CCI [REDACTED]

[REDACTED]	[REDACTED]	[REDACTED]	[REDACTED]	[REDACTED]	[REDACTED]	[REDACTED]	[REDACTED]	[REDACTED]
[REDACTED]	[REDACTED]	[REDACTED]	[REDACTED]	[REDACTED]	[REDACTED]	[REDACTED]	[REDACTED]	[REDACTED]
[REDACTED]	[REDACTED]	[REDACTED]	[REDACTED]	[REDACTED]	[REDACTED]	[REDACTED]	[REDACTED]	[REDACTED]
[REDACTED]	[REDACTED]	[REDACTED]	[REDACTED]	[REDACTED]	[REDACTED]	[REDACTED]	[REDACTED]	[REDACTED]
[REDACTED]	[REDACTED]	[REDACTED]	[REDACTED]	[REDACTED]	[REDACTED]	[REDACTED]	[REDACTED]	[REDACTED]
[REDACTED]	[REDACTED]	[REDACTED]	[REDACTED]	[REDACTED]	[REDACTED]	[REDACTED]	[REDACTED]	[REDACTED]

[REDACTED]

[REDACTED]

CCI [REDACTED]

CCI [REDACTED]

[REDACTED]

[REDACTED]

CCI

[REDACTED]

[REDACTED]

[REDACTED]

[REDACTED]

[REDACTED]

[REDACTED]

[REDACTED]

[REDACTED]

CCI [REDACTED]

[REDACTED]	[REDACTED]	[REDACTED]	[REDACTED]	[REDACTED]
[REDACTED]	[REDACTED]	[REDACTED]	[REDACTED]	[REDACTED]

CCI [REDACTED]

CCI [REDACTED]

6.5. Baseline and Other Summaries and Analyses

6.5.1. Study Conduct

6.5.1.1. Subject Disposition, Vaccination Administration, and Blood Samples

The number and percentage of subjects who are randomized will be included in the disposition summary. Screen failures and reasons for screen failure may be included in a separate tabulation.

Subjects who received each vaccination and who are included in each study population (safety; mITT-1 through mITT-3; PP-2 and PP-3) will be summarized. Subjects completing the study as well as those who withdrew during the vaccination phase, who completed the vaccination phase, and who withdrew prior to the end of the study will be reported along with the reasons for withdrawal.

For each blood draw, the numbers and percentages of subjects randomized, vaccinated at each visit (Visits 1, 2, and 4), and providing blood samples within the protocol-specified time frame, as well as before and after the specified time frame, will be tabulated.

Summary tables will be presented for each randomized vaccine group and total population.

Listings will be provided for the following:

- Subjects' noncompliant vaccine administration
- Protocol violations
- Subjects receiving the vaccine not as randomized
- Subjects receiving vaccine who were not randomized
- Subjects with temporary delays to vaccine administration
- Subjects who withdrew from the study and reasons for withdrawal
- Subjects who withdrew because of AEs
- Subjects included or excluded from each analysis population and reasons for exclusion

6.5.1.2. Demographic, Medical History, and Baseline Characteristics

Variables defined in [Section 3.8.2](#) will be reported according to Pfizer standard summary reporting. Summaries will be provided for each vaccine group separately. Demographic and baseline characteristic summaries may also be generated for different analysis sets as defined in [Section 4](#).

Medical history reports will be provided by vaccine group.

6.5.2. E-Diary Completion

E-diary compliance as defined in [Section 3.8.1](#) will be summarized for each dose by vaccine group and total compliance using descriptive statistics. The safety population will be used to generate the summary reports. The denominator for the e-diary compliance rates will be the total number of subjects who received the specific vaccination.

6.5.3. Nonstudy Vaccine and Concomitant Medications

Nonstudy vaccines and concomitant medications captured throughout the study will be descriptively summarized for subjects in the overall safety population.

6.6. Analysis for Other Safety Endpoints

All safety data will be summarized according to vaccine received. The safety population will be used for the analysis. The percentage of subjects reporting the defined events will be summarized with exact 2-sided 95% CIs by vaccine group.

6.6.1. Physical Examinations and Vital Signs

Physical examinations and vital signs may be recorded on the CRF prior to receiving the first dose of investigational product. Data listings will be provided in accordance with Pfizer reporting standards.

6.6.2. Drug-Induced Liver Injury

For cases meeting the criteria of liver injury as defined in Section 8.4.2 of the study protocol, a listing will be provided.

6.7. Subgroup Analysis for Efficacy and Safety Endpoints

Subgroup analyses based on age category (see [Table 2](#)), race, ethnicity, and sex will be performed on all primary and secondary efficacy endpoints (as supplemental analysis) as well as the primary safety endpoints. Furthermore, supplemental analyses include region (North America; South America; Oceania; East Asia including Japan, South Korea, and Taiwan; Japan [by itself]; and Europe), comorbidity at baseline, healthcare exposure at baseline, and prior systemic antibiotic exposure will be performed on the primary and secondary efficacy endpoints.

The comorbidity subgroup will include subjects who have any of the following, which will be pooled together for analysis, at study entry:

1. Chronic lung disease (eg, chronic obstructive pulmonary disease [COPD], asthma, emphysema, chronic bronchitis)
2. Congestive heart failure
3. Inflammatory bowel disease
4. Renal disease
5. Diabetes
6. Deficiency anemia

The healthcare exposure subgroup will include the following prior or anticipated healthcare exposure and will be presented for each exposure risk separately:

1. Previous hospitalization
2. Outpatient visits (includes emergency room and healthcare provider)
3. Skilled nursing facilities or nursing home residence
4. Inpatient hospitalization >2 nights' duration scheduled >37 days after randomization

Additionally, categories based on 2 or more, 3 or more, and all of the above will be presented.

The prior systemic antibiotic exposure subgroup will include subjects who have received systemic (ie, oral or injected) antibiotics at any time in the 12 weeks prior to study entry.

The above subgroup analyses will be performed on the mITT-3/mITT-2 population and are to be considered supportive assessments.

An additional supplemental analysis deriving VE and its 95% CI may be provided for the incidence of a first primary episode of CDI based on case definition 1 for subjects in the mITT-1 population.

Safety endpoints will be further described by race, age categories, and sex in a similar approach as discussed in [Section 6.1.2](#).

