4.1. Inclusion Criteria

Subjects must meet all of the following inclusion criteria to be eligible for enrollment into the study:

1. Evidence of a personally signed and dated ICD indicating that the subject has been informed of all pertinent aspects of the study.
2. Willing and able to comply with scheduled visits, vaccination plan, and other study procedures.
3. 50 Years or older at enrollment.
4. Subjects with an increased risk of future contact with healthcare systems by virtue of:
 - At least 1 inpatient hospitalization ≥ 2 nights' duration in the previous 12 months; or
 - At least 2 emergency room visits in the previous 12 months; or
 - At least 10 outpatient visits (primary and/or secondary care visits; defined as an in-person visit to the office/clinic of a prescribing healthcare provider for the purposes of the diagnosis, treatment, or ongoing management of a medical condition, excluding pharmacy and mental health visits) in the previous 12 months; or
 - Residence in a skilled nursing facility (a residential institution that provides professional nursing care and rehabilitation services, usually following discharge from the hospital); or
 - Residence in a nursing home (a residential institution that provides assistance with activities of daily living); or
 - Inpatient hospitalization ≥ 2 nights' duration scheduled ≥ 37 days after randomization.

Or subjects who have received systemic (ie, oral or injected) antibiotics for a minimum of 48 hours at any time in the previous 12 weeks.
5. Ability to be contacted by telephone during study participation.
6. Negative urine pregnancy test for female subjects of childbearing potential.

Female subjects of nonchildbearing potential must meet at least 1 of the following criteria:

- a. Achieved postmenopausal status, defined as follows: cessation of regular menses for at least 12 consecutive months with no alternative pathological or physiological cause; status may be confirmed with a serum follicle-stimulating hormone (FSH) level confirming the postmenopausal state;
- b. Have undergone a documented hysterectomy and/or bilateral oophorectomy;
- c. Have medically confirmed ovarian failure.

All other female subjects (including female subjects with tubal ligations) are considered to be of childbearing potential.

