	Inpatient hospitalization ≥2 nights' duration scheduled ≥37 days after randomization.
	Received systemic (ie, oral or injected) antibiotics at any time in the previous 12 weeks.

Subjects withdrawn from the study after randomization will not be replaced, regardless of the reason for withdrawal.

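### SAP 6.7 defines the scheduled-hospitalization subgroup as more than 2 nights and more than 37 days, against ≥2 and ≥37 in protocol criterion 4 and SAP Table 3

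*SAP*

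**What the plan says.** Three places state the scheduled-hospitalization condition.

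- Protocol 4.1, inclusion criterion 4: "Inpatient hospitalization ≥ 2 nights' duration scheduled ≥ 37 days after randomization".
- SAP 2.2.2, Table 3, in the rows headed as inclusion criterion 4: "Inpatient hospitalization ≥2 nights' duration scheduled ≥37 days after randomization".
- SAP 6.7, item 4 of the healthcare-exposure subgroup: "Inpatient hospitalization >2 nights' duration scheduled >37 days after randomization".

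SAP 6.7 reports each of the four exposures separately on the primary and secondary efficacy endpoints. It then adds categories for subjects with two or more, three or more, and all of them. On status it says: "The above subgroup analyses will be performed on the mITT-3/mITT-2 population and are to be considered supportive assessments".

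**The concern.** The SAP gives two definitions of one exposure, and the one that governs the subgroup analysis is not the one that governed enrollment. Two nights is the shortest stay that criterion 4 accepts, so the strict inequality removes a whole class of eligible subjects, in addition to those scheduled for day 37 itself. No reason is given for a stricter rule. The numbers 2 and 37 are those of criterion 4; only the signs differ.

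What is at stake is the meaning of a few supportive vaccine-efficacy estimates. A reader of the report would take this subgroup to be the people enrolled because of a planned admission, and it would not be. Item 4 also feeds the combined categories, so the discrepancy does not stay in one row. If nobody settles the definition, a programmer has to choose between two statements in the same SAP.

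**Working it through.** The plan gives no figure to reproduce here. The check is a comparison of two rules at their boundary.

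**Inputs**
- Rule A (protocol criterion 4 and SAP Table 3): nights ≥ 2 and day ≥ 37.
- Rule B (SAP 6.7 item 4): nights > 2 and day > 37.

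**Step 1. Boundary cases**

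| Nights | Day | Rule A | Rule B |
|---|---|---|---|
| 1 | 36, 37 or 38 | no | no |
| 2 | 36 | no | no |
| 2 | 37 | yes | **no** |
| 2 | 38 | yes | **no** |
| 3 | 36 | no | no |
| 3 | 37 | yes | **no** |
| 3 | 38 | yes | yes |

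**Step 2. General form.** Nights and days are whole numbers, so rule B is nights ≥ 3 and day ≥ 38. Everyone who meets B meets A, so B adds nobody. Those who meet A but not B are subjects with exactly 2 nights (any day from 37 on) together with subjects on exactly day 37 (any stay of 2 nights or more). The three mismatches in the table are grid points, not a share of subjects.

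**Step 3. Carry-through to the combined categories.** Let k be the number of the other three exposures that an affected subject has. The count is k + 1 under rule A and k under rule B.

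| k | Count under A | Count under B | Effect |
|---|---|---|---|
| 0 | 1 | 0 | in none of the four exposure subgroups |
| 1 | 2 | 1 | leaves two or more |
| 2 | 3 | 2 | leaves three or more |
| 3 | 4 | 3 | leaves all four |

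Every affected subject with k of at least 1 therefore drops out of exactly one combined category.

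**Step 4. Number affected.** This would need the number of subjects with a planned stay and the distribution of planned nights and days. Neither document gives either, so no count follows.

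**The case against.** **SAP 6.7 does not claim to copy criterion 4.** Its item on previous hospitalization has no minimum stay. Its outpatient item merges emergency-room and provider visits and drops the thresholds of 2 and 10. Skilled nursing facilities and nursing homes are pooled. This stands as a general point: a baseline exposure group may differ from an eligibility rule. It does not rescue item 4, which repeats both of the criterion's numbers and changes only the signs, against Table 3 of the same document.

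**Nobody may be lost in practice.** The SAP introduction says that programming rules are prepared separately. If the flag is taken from a criterion-4 tick box, the strict inequality could not be applied. That is fair: the documents show what the text prescribes, not what the program does. Likewise, if the signed SAP prints ≥ on this line, the point falls away. The sign does appear elsewhere in the SAP, including in Table 3.

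**A reader might infer that the antibiotic subgroup has the same fault.** The protocol requires "antibiotics for a minimum of 48 hours at any time in the previous 12 weeks". SAP 6.7 says "antibiotics at any time in the 12 weeks prior to study entry", and Table 3 says "Received systemic (ie, oral or injected) antibiotics at any time in the previous 12 weeks". Here, however, the SAP rule is the wider one. Courses of 48 and 72 hours meet both rules; courses of 24 and 47 hours meet only the SAP rule. Everyone enrolled by the antibiotic route is in the subgroup. The only addition is subjects who entered by another route and had less than 48 hours of antibiotics. For a subgroup of prior exposure that is a legitimate definition, and it matches the Table 3 monitoring category. The amendment history says that Amendment 4 clarified antibiotic use for this criterion, but it does not show that the 48-hour wording arose then. What remains is small: the SAP does not say that any exposure is intended, and Table 3 restates criterion 4 without its minimum duration.

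**A reader might also infer a large loss, or a visible shift in subgroup efficacy.** The documents do not support either. They give no lengths of planned stay and no subgroup counts. The targets of 40 and 66 cases refer to the per-protocol-3 population, whereas these subgroups use mITT-3 and mITT-2.

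**Conclusion.** SAP 6.7 item 4 is wrong as written on scheduled hospitalization. It contradicts the protocol and the SAP's own Table 3, and it excludes subjects with exactly 2 planned nights or a stay on exactly day 37. The direction is certain: the subgroup can only shrink, and the combined categories can only be under-counted. The number affected is unknown.

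The consequence is minor. The analyses are supportive and carry no success criterion or alpha. The conclusion assumes that the text is applied literally and that the data capture can tell 2 nights from 3 and day 37 from day 38. It does not extend to the antibiotic subgroup.

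**What to change.** In SAP 6.7, healthcare-exposure item 4, change > 2 nights to ≥ 2 nights and > 37 days to ≥ 37 days, before unblinding, and check that the programming specification uses the same rule. This changes two signs, needs no new data and touches no hypothesis test.

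Optionally, in the same revision, add one sentence saying that the antibiotic subgroup means any systemic exposure in the 12-week window, if that is the intent, and reconcile the Table 3 antibiotic row with the protocol's wording of criterion 4. This is a clarification and not part of the correction.
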